### **3.3 Primary Study Endpoints**

The primary endpoint of this study will examine the safety, feasibility and efficacy of n-3 PUFAs/Vitamin D to improve chronic pain outcomes following major thermal burn injury. **Outcome to assess safety:** Safety outcomes will be met after descriptive review of adverse outcomes, and comparison of adverse events is made across treatment groups by investigative team at the conclusion of the study. **Outcome to assess feasibility:** 60 patients will be enrolled, randomized into one of 4 treatment arms in a 1:1:1:1 ratio, and treated with study drug for 6 weeks following Major Thermal Burn injury severe enough to warrant surgery within a 24 month period. Proportion of participants completing following up at 6 weeks will be reported. The concentration of Vitamin D and n-3 PUFAs will be calculated before and after the 6 week treatment in each treatment arm to assess the response (expect an increase in both Vitamin D and n-3 PUFA in treatment arms). **Outcome to assess efficacy:** Efficacy of Vitamin D/PUFA will be measured by difference in pain severity in treatment arms versus control arms. We will 1) calculate a model estimated mean of chronic pain severity and corresponding 95% Confidence interval in each study group and 2) determine the slope of pain recovery among individuals treated with Vitamin D and n-3 PUFAs relative to control participants using a linear mixed model adjusting for sex, ethnicity, and study site.

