
## **6 Statistical Plan**

### **6.1 Sample Size Determination**

The purpose of this study is to assess study feasibility, safety and to obtain initial effect size estimates and confidence intervals to use in sample size calculations for a larger study. Previous studies of Vitamin D and n-3 PUFAs for the treatment of chronic pain are poorly generalizable to this setting because 1) they examine treatment of established chronic pain states versus developing pain states, 2) do not involve trauma exposure/acute stress, and 3) are not preventive studies. Therefore, this pilot study will be instrumental in demonstrating feasibility and safety of the protocol, and estimates of efficacy along with confidence intervals will be helpful for planning a larger follow-up study.

**Justification for the sample size.** We will target 15 individuals in each group (60 total) so that feasibility and safety may be determined as well as provide potential evidence for efficacy. Below, calculations are provided to justify sample size for each objective.

**Feasibility:** Assuming that observed follow-up will be around 80%, this study will allow us to estimate follow-up rates to within  $\pm 10\%$  with a 95% confidence interval given we reach the enrollment target of 60. Allowing for up to 20% loss, with 30 participants treated in each n-3 PUFA arm of our study, our study is powered at 90% to detect a difference of 2.6% of DHA (an n-3 PUFA) in total fatty acid content considering a standard deviation of 1.3%. This study (30 per Vitamin D arm) is powered at 83% to detect a change of 9 ng/dl in Vitamin D level assuming a SD of 10.5.

**Efficacy:** Allowing for up to 20% loss and assuming a common standard deviation of 2.6 (approximated from our pilot dataset) and no interaction between treatments, randomizing 30 participants to each comparison group (Vitamin D/n-3 PUFA versus control) will allow us to estimate the difference in mean pain severity to within  $\pm 1.4$  using a two-sided 95% confidence interval.

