**Efficacy:** Estimates of efficacy will be obtained via repeated measures analysis using mixed effects models (PROC MIXED in SAS 9.4). Prior to unblinding the data, our study statistician will perform a blind review of the data in which statistical models will be developed and tested using dummy (computer generated) treatment assignments. The goal of this is to fit the most appropriate model given aggregate data. Graft site pain severity will be collected in four waves across time; therefore, we will use mixed effects modeling with random error using an unstructured covariance matrix. The model will include fixed effects for PUFA, Vitamin D, their interaction, time, and the interactions between groups and time, as well as fixed effects for site, gender, and race/ethnicity. During blind review, competing nested fixed effect models will be compared. We will consider modeling time using either a) time as continuous variable with a linear model (i.e., slopes only), b) time as a continuous variable with a higher order polynomial model (up to cubic, given 4 time points), or c) time as a class variable. Competing fixed effect models will be fitted using maximum likelihood and compared using the BIC criterion. Once the form for the fixed effect model is selected, the final model will be fit using restricted maximum likelihood. After unblinding the data, we will use appropriately specified linear contrasts of the model parameters to estimate mean differences across groups at each time point along with 95% confidence intervals.

**Interim analysis:** Two interim analyses are planned after the enrollment of the 20th and 40th patients in the study. This will be conducted to ensure safety, perform a feasibility assessment, and assess potential efficacy. This optimizes study ethics, as it ensures safety of current and future study participants, allows

optimization of study protocol based on results of safety and feasibility assessment, and allows an efficacy assessment with appropriate statistical “penalty” for an interim look. Adverse events will be qualitatively reviewed at two interim analyses occurring after enrollment of the 20th patient and after enrollment of the 40th patient. While study investigators, staff, and participants remain blinded, the study statistician will prepare a qualitative summary of adverse events by type over the treatment groups. The results will be reported to investigators in aggregate such that blinding is maintained.

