Significance thresholds for interim analyses for potential efficacy will be adjusted using the O’Brien-Fleming approach. In order for the trial to stop enrolling because efficacy (superiority) is established after the first interim analysis (after 20 patients enrolled), the boundary critical value of 3.428 and corresponding alpha of 0.0006 must be reached. In order for the trial to stop enrolling because efficacy is established after the second interim analysis (after 40 patients enrolled), the boundary critical value of 2.431 and corresponding alpha of 0.0151 must be crossed. After the final analysis (third analysis) a critical value of 1.985 and a p-value of 0.0471 will be used. This final, adjusted p-value threshold of 0.0471, allows for a statistical “penalty” to be assessed because of the interim look. Given that this is a pilot study, we believe it is critically important to assess our safety, feasibility and potential efficacy outcomes at interim analysis.

Given that the study was terminated early after enrollment of the 24th patient after one interim analysis, the final, adjusted p-value threshold of 0.0492, allows for a statistical “penalty” to be assessed because of the interim look.

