### **6.3 Subject Population(s) for Analysis**

We will examine effect of n-3 PUFA, Vitamin D, and n-3 PUFA+Vitamin D treatment on pain outcomes using the following populations; however, the All-randomized population will be the primary analysis performed in this study following an intention to treat paradigm.

Primary Analysis:

- All-randomized population: Any subject randomized into the study, in the group to which they were randomized, regardless of extent of study drug received (intention-to-treat).

Secondary Analyses:

- Protocol-compliant population: Any subject who was randomized and maintained  $>80\%$  study medication adherence, and no major protocol violations.

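### Does the final efficacy threshold of 0.0492 need a named contrast and visit before it can be used?

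*Combined protocol and SAP*

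**What the plan says.** The interim-analysis text in section 6.2 sets O'Brien-Fleming thresholds for potential efficacy. "In order for the trial to stop enrolling because efficacy (superiority) is established after the first interim analysis", at 20 enrolled, the statistic has to reach 3.428 (alpha 0.0006). The second look, at 40 enrolled, has 2.431 (0.0151), and the planned final analysis has 1.985 (0.0471). The section then records termination at the 24th patient and states that, "after one interim analysis, the final, adjusted p-value threshold of 0.0492" is the penalty for the interim look. None of these values is tied to a visit or a contrast.

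The other places that bear on the target are:

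- **Section 6.2, Efficacy.** "Estimates of efficacy will be obtained via repeated measures analysis using mixed effects models". The outcome is graft-site pain. The model has both supplements, their interaction, time and group-by-time terms. Blind review chooses whether time is linear, polynomial or a class variable. After unblinding, "we will use appropriately specified linear contrasts of the model parameters to estimate mean differences across groups at each time point", with 95% confidence intervals.
- **Section 3.3.** Efficacy is the difference in pain severity between treatment and control arms. The section asks for group means and also to "determine the slope of pain recovery among individuals treated with Vitamin D and n-3 PUFAs relative to control participants".
- **Section 6.1.** The stated purpose includes "to obtain initial effect size estimates and confidence intervals to use in sample size calculations for a larger study". The efficacy precision statement concerns 30 participants per comparison group, each supplement against its control, on mean pain severity, assuming no interaction.
- **Section 6.3.** "the All-randomized population will be the primary analysis performed in this study following an intention to treat paradigm".

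**The concern.** A significance threshold protects against false positives only for the test it is attached to. Here the outcome, model and population are fixed, but the visit is not, nor is the choice between a mean and a slope. The pooled comparison per supplement is implied in section 6.1 but never linked to 0.0492. With four follow-up visits and two supplements, eight differences could each be held against the same threshold. The contrasts are applied after unblinding, so the most favourable visit could in principle be presented as the result. The penalty in 0.0492 is for the interim look and would not cover that selection. At stake is a larger trial planned on a chance finding.

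**Working it through.** **Inputs from the documents.** First-look boundary 3.428 at 20 enrolled; final threshold 0.0492 at 24 enrolled; four visits (6 weeks, then 3, 6 and 12 months); two supplements.

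**Assumed, because the documents do not give them.** First-look information fraction t (1/3, 1/2 or 20/24); correlation between visits within a patient (0.3 to 0.9, equal for all pairs); and, in step 4, a rule that any significant visit counts.

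**1. Boundaries against their p-values.** With p = 2(1 − Φ(z)): 3.428 gives 0.0006, 2.431 gives 0.0151 and 1.985 gives 0.0471, all as stated. A p-value of 0.0492 corresponds to z = 1.967.

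**2. Can 0.0492 be reproduced?** Solve for the final p that makes the overall two-sided error 0.05, with correlation √t between the looks.

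| First look | t = 20/24 | t = 1/2 | t = 1/3 |
|---|---|---|---|
| 3.428 held fixed | 0.0500 | 0.0499 | 0.0497 |
| O'Brien-Fleming shape | 0.0429 | 0.0480 | 0.0497 |
| Lan-DeMets O'Brien-Fleming spending | 0.0392 | 0.0478 | 0.0497 |

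No variant returns 0.0492 exactly. Given the stated 3.428, it lies slightly on the cautious side. A boundary re-derived for t = 20/24 would need a smaller final p, but that goes with a first-look z of 2.218, which is not what the plan states.

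**3. Error for one named test.** Error = 1 − P(|Z₁| < 3.428 and |Z₂| < 1.967), correlation √t. The result is 0.0492 at t = 20/24, 0.0493 at t = 1/2 and 0.0495 at t = 1/3. The threshold therefore does what the section claims for it.

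**4. Error if any visit could count.** If the four visits were independent, the final look alone would give 1 − (1 − 0.0492)⁴ = 0.183. Simulation with correlated visits (400,000 draws, t = 20/24) gives:

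| Correlation | 0.3 | 0.5 | 0.7 | 0.9 |
|---|---|---|---|---|
| One supplement, any of 4 visits, time as class | 0.172 | 0.153 | 0.129 | 0.092 |
| One supplement, any of 4 visits, linear time | 0.107 | 0.096 | 0.084 | 0.069 |
| Either supplement, any of 8, time as class | 0.313 | 0.283 | 0.241 | 0.176 |

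A separate simulation of the final look alone gave 0.171, 0.153, 0.128 and 0.093 for the first row. A check with 24 patients, six per arm, and t-tests on 20 degrees of freedom gave 0.173, 0.155, 0.132 and 0.094. That check has no missing data and no covariates, so it is simpler than the planned model.

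**5. How much belongs to the choice of visit.** Two independent supplement tests at one named visit already give 1 − (1 − 0.0492)² = 0.096. Naming a visit or a time average would leave that in place. With a visit-averaged contrast per supplement, the 24-patient check gives 0.095-0.096 for either supplement. The part attributable to the unnamed visit is therefore the one-supplement row, 9-17% against 4.9%, and not the eight-contrast row.

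**The case for a change.** The best case for a change is that the plan did not stay with estimation. Section 3.3 lists efficacy among the primary endpoints. Section 6.2 bars p-values and confidence intervals for comparing arms on safety but sets no such bar for efficacy. The threshold was recalculated after termination, so it is evidently meant to be used. Blind review settles the form of time and the fixed effects, not the contrast or the visit. One sentence in the SAP would close the gap.

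The missing specification stands. If the analysts add that sentence before unblinding, nothing is lost.

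The rest carries less weight. The inflated figures need a rule under which any favourable visit establishes efficacy, and the documents contain no such rule. The planned output is every visit's difference with its interval, so an isolated result at one visit would be seen beside the other three. Section 6.1 already indicates the pooled comparison per supplement. The stopping boundaries no longer operate, because enrolment has ended; only the final threshold is live.

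Nor is there one clearly better target to write in. A visit average can dilute an effect confined to one visit. A late visit suits a chronic-pain question but discards the earlier visits, and a slope answers a different question from a mean. Dropping the threshold instead would undo a choice the sponsor made deliberately.

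**Conclusion.** No change to the plan is called for. The threshold lacks a named visit or time summary, but this is a detail that analysts can fill sensibly from section 6.1 and the mixed model, and the choice among candidates is a fair trade-off. For a single test the error is about 4.9% (0.0492 to 0.0495 over the information fractions tried), given a first look at 3.428. The figure of 9-17% for one supplement with time as class, or 7-11% with linear time, depends on an any-visit rule that the plan does not state and on an assumed correlation of 0.9 to 0.3. Section 2 makes feasibility and safety the primary objective and puts potential efficacy second, so a reader should treat any single-visit result below 0.0492 as an estimate for planning. The derivation of 0.0492 is not shown and was not reproduced exactly, but with the stated first-look boundary this does no harm.

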#### **Secondary Analyses:**

Similar models as for the primary outcome will be fit for both the Brief Pain Inventory and the SF-12 Mental and Physical Component Scale Scores.

**Sex as a biological variable (SABV)** will be examined in treatment response including sex-by treatment interaction terms in the mixed effect model specified above and exploring sex differences in therapeutic response to Vitamin D and n-3 PUFAs.

**General mental and physical health** will be assessed using SF-12 physical and mental component scores (PCS and MCS) and the impact on physical and mental functioning will be determined in each of the treatment groups. A clinically important reduction in SF-12 PCS and MCS ranges between 2.5-4.5; therefore, a reduction of  $\geq 4.5$  will be considered a clinically significant improvement MCS/PCS.

**Brief Pain Inventory:** We will also use multivariable analysis to determine the role of n-3 PUFA/Vitamin D supplementation in pain interference using composite and individual measures of the Brief Pain Inventory.

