**Secondary Objectives:**

[figure not shown]
1. To demonstrate potential efficacy of n-3 PUFAs/Vitamin D on decreasing graft site pain severity in survivors of MThBI requiring surgery. This will provide data on the confidence interval around our model estimates, which will inform a larger clinical trial.
2. Demonstrate the potential efficacy of n-3 PUFAs/Vitamin D on reducing pain interference on important domains of life function measured by the Brief Pain Inventory and SF-12 Mental and Physical Component Scores.
3. To demonstrate the utility of a clinical prediction tool based on a logistic function derived from a previous observational cohort study to enhance enrollment of a population of MThBI survivors at greater risk of chronic pain development.
4. To explore sex as a biological variable to determine whether there are differences in safety and efficacy among women and men.

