Demographic and phenotypic data will be collected at this time. Patients will be asked to report demographic information including age, sex, ethnicity, education level, income level, and marital status. Pre-burn physiological traits will be assessed using pain catastrophizing, SF12 MCS, depression anxiety stress scale (DASS21), and Life events checklist. Characteristics of the patients' injuries will be reported through estimated percent total body surface area, mechanism their burn, and the donor/graft site location. Current pain at the graft site will be assessed using a 0-10 numeric rating scale, brief pain inventory, DN-4, S-LANSS and Regional Pain Scale (RPS). The patient's physical function will be assessed with the SF12 and a work/disabilities questionnaire. Depressive symptoms will be recorded using the DASS21. PTSD symptoms will be assessed with the PTSD Symptom Severity index-interview. Patient somatic symptoms will be recorded with the somatic symptoms inventory. The patient's burn wound will be documented with digital photos taken of the injury site. Dissociative symptoms will be documented with the Michigan Critical Events Perception Scale. Analgesic medication use will be recorded as daily milligram morphine equivalents. All patient information will be recorded by a trained research assistant or principal investigator. We additionally will assess treatment expectation using a modified survey that uses Likert scales prior randomization.

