**Primary study measures by timepoint.**

Domain	Measure	D1	6W	3M	6M	1Y
Demographic information	Age, sex, ethnicity, education level, income level, marital status	•				
Pre-burn psychological traits	Pain catastrophizing, SF12 MCS, DASS21, Life events checklist	•				
Burn Injury Characteristics	Estimated % TBSA, mechanism of burn, donor/graft site location	•				
Graft Site Pain severity	0-10 numeric rating scale; Brief Pain Inventory, DN-4, S-LANSS  †RPS	•	•	•	•	•
Physical function	SF12, work/disability questions	•	•	•	•	•
Depressive Symptoms	Depression anxiety stress scale (DASS21)	•	•	•	•	•
PTSD symptoms	PTSD Symptom Severity index-interview	•	•	•	•	•
Somatic Symptoms	Somatic symptoms inventory	•	•	•	•	•
Alcohol and drug use	TWEAK/SAOM		•	•		•
Burn wound evaluation	Digital photos of injury/wound site	•	•	•	•	•
Dissociative Symptoms	Michigan Critical Events Perception Scale	•				
Analgesic Medication Use	Daily milligram morphine equivalents, non-opioid analgesic use	•	•	•	•	•

†RPS = Regional pain scale, M=month, W=week, D= day, PTSD=post-traumatic stress disorder, TBSA: total body surface area, DN-4 Douleur Neuropathique 4, neuropathic pain questionnaire, S-LANSS: self report version of the Leeds Assessment of Neuropathic Pain scale SF-12: 12 item short form from the medical outcomes survey.

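### The 4.5-point SF-12 criterion has no reference visit, unit or control comparison; read arm by arm, it would mix shared recovery with any supplement effect

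*Combined protocol and SAP*

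**What the plan says.** Secondary Objective 2 (Section 2) is comparative in intent: "Demonstrate the potential efficacy of n-3 PUFAs/Vitamin D on reducing pain interference on important domains of life function", with the SF-12 component scores among the measures.

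Section 6.2, Secondary Analyses, deals with SF-12 twice. The opening sentence says "Similar models as for the primary outcome will be fit for both the Brief Pain Inventory and the SF-12 Mental" and Physical scores. The primary efficacy model is described earlier in Section 6.2: "The model will include fixed effects for PUFA, Vitamin D, their interaction, time, and the interactions between groups and time", plus site, gender and race/ethnicity. Its linear contrasts give mean differences between groups at each time point with 95% confidence intervals.

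A later paragraph on general mental and physical health says "the impact on physical and mental functioning will be determined in each of the treatment groups". It then cites a range: "A clinically important reduction in SF-12 PCS and MCS ranges between 2.5-4.5". From this it concludes that a reduction of at least 4.5 "will be considered a clinically significant improvement MCS/PCS".

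On the enrollment measurement, Section 5.1 begins its list with "Pre-burn physiological traits will be assessed using pain catastrophizing" and includes SF12 MCS in the same sentence. The table of study measures has a pre-burn psychological traits row, "Pain catastrophizing, SF12 MCS, DASS21, Life events checklist", marked at D1 only. The same section and table also list the SF12 under physical function, at D1 and at all four follow-up visits, with no pre-burn label.

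**The concern.** The 4.5-point sentence is the only statement of clinical importance for SF-12, and three things needed to apply it are missing: the visit from which change is measured, whether the change is a patient's or a group mean's, and a comparison with control. Its neighbouring sentence speaks of results in each group, so a natural way to apply it is to look at each arm and ask whether it moved by 4.5 points.

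Patients recover from a burn over a year whatever they are given. A change from a post-burn visit such as week 6 contains that recovery. Week 6 is also the end of the treatment period, so such a change would miss any benefit already gained by then. A change in MCS from a pre-burn value contains the injury effect as well: an arm whose mental health was fully preserved would show a mean change near zero. In neither case does one arm's change isolate what the supplement did. At stake is whether recovery in a treated arm could be reported as a clinically significant improvement.

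**Working it through.** **1. Figure to reproduce.** There is none. The 4.5-point limit comes from a cited source, and the documents give no SD, power or precision for SF-12. The SDs and shifts below are assumptions.

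**2. The two SF-12 statements side by side.**

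| Feature | Mixed model (opening sentence) | 4.5-point rule (later paragraph) |
|---|---|---|
| Quantity | Mean difference between groups | A change |
| Time | Each time point | Not stated |
| Unit | Group mean | Not stated |
| Control comparison | Yes, by linear contrasts | Not stated |
| Baseline score | Not among the listed terms | Not stated whether D1 is the reference |

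Nothing links the right-hand column to the left.

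**3. Patient-level reading, no supplement effect.** Let the change be normal with a shift common to all arms. Then P(change ≥ 4.5) = 1 − Φ((4.5 − shift)/SD). For example, with shift 3 and SD 10: 1 − Φ(0.15) = 0.440.

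| Common shift | SD 8 | SD 10 | SD 12 |
|---|---|---|---|
| 0 | 0.287 | 0.326 | 0.354 |
| +3 | 0.426 | 0.440 | 0.450 |
| +6 | 0.574 | 0.560 | 0.550 |
| +10 | 0.754 | 0.709 | 0.677 |

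If the reference is a pre-burn score and patients remain on average 3 points below it, the share is 0.17 to 0.27; at 8 points below, 0.06 to 0.15. Every figure is the same in placebo and active arms, and the expected between-arm difference is 0 in each row.

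The calculation counts gains, although the SAP words the change as a reduction. By symmetry the same shares apply to falls under a common downward shift. The SAP calls a reduction an improvement, while Section 3.4 aims to improve health on these scores, so the direction needs reconciling too.

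**4. Group-mean reading, no supplement effect.** P(arm mean ≥ 4.5) = 1 − Φ((4.5 − shift)/(SD/√n)). Take SD 10:

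- Planned 15 per arm: 0.28 at shift 3, 0.72 at shift 6.
- About 6 per arm (24 enrolled ÷ 4 arms, if balanced): 0.36 at shift 3, 0.64 at shift 6.

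The unit therefore changes the answer as well.

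**5. What the between-arm contrast can deliver.** The 95% half-width is 1.96 × SD × √(2/n), with n patients on each side of one factorial comparison and no loss to follow-up.

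| n per side | SD 8 | SD 10 | SD 12 |
|---|---|---|---|
| 30 (as planned) | 4.05 | 5.06 | 6.07 |
| 12 (24 enrolled ÷ 2) | 6.4 | 8.0 | 9.6 |

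At 12 per side, a lower limit above 4.5 needs an estimate above 4.5 + 6.4 = 10.9 (SD 8) to 4.5 + 9.6 = 14.1 (SD 12). With SD 10 and no effect, the estimate alone lies 4.5 or more from zero in either direction with probability 2 × (1 − Φ(4.5/(10 × √(2/12)))) = 0.27. The interval, not the point estimate, has to be read against the limit.

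**The case against.** The strongest reply is that the plan already has the right analysis. The opening sentence of Secondary Analyses carries the primary mixed model over to MCS and PCS, and that model estimates between-group differences with confidence intervals. This stands. A reader might infer that the SF-12 analysis as a whole measures injury and natural recovery instead of a supplement effect. The documents do not support that: with randomization and a concurrent placebo arm, a shared shift falls on all arms equally in expectation and cancels in the planned contrast.

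Nor do the documents say that the limit will be judged within each arm. Results determined by group may simply be the inputs to a comparison, and the 4.5-point sentence names no arm. Judging within arms is an inference from wording and position.

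A reader might also take D1 as the reference and treat it as pre-burn for both scores. No section names D1 as the reference. The pre-burn label is shown for MCS only, and the SF12 under physical function at D1 carries no such label.

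Finally, the lowest and highest shares in the working, 6% and 57% across deficits of 3 to 8 points and recoveries of 3 to 6 points, should not be read as the effect of choosing a reference visit. They also vary the assumed recovery, deficit and SD.

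Another fair point is that the limit's source, a spine-surgery study of minimum important differences, may have derived it for change within patients, and the documents do not say. This is a reason to state how the limit is used, and to keep any patient-level proportions comparative.

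**Conclusion.** The concern holds as a gap in specification. The SF-12 clinical-importance rule lacks a reference visit, a unit and a comparison with control, and is not tied to the between-arm model planned in the same section. If it is applied arm by arm, then with no supplement effect about 43% to 57% of patients in any arm would pass, given a common recovery of 3 to 6 points, an SD of change of 8 to 12 points and normality; none of these values comes from the documents. For MCS, change from the score named at D1 would include the injury effect as well.

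The planned between-arm estimate remains unbiased. Its remaining weakness is that the listed model terms omit a baseline score that is collected before randomization and could improve precision.

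The consequence is limited: SF-12 is a secondary outcome of a pilot, and the feasibility criteria in Section 6.2 do not depend on it. The correction is still worth making because this rule is what would turn an SF-12 result into a claim of clinical improvement.

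**What to change.** Amend the general mental and physical health paragraph of Section 6.2 in three respects.

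- **Limit.** Interpret the 4.5-point limit against the estimated difference between each supplement and its control at each follow-up visit, from the SF-12 mixed model already planned, and report the 95% confidence interval against it. State the direction that counts as improvement.
- **Baseline.** Add the D1 SF-12 score as a covariate in the MCS and PCS models, and state for each whether the D1 score refers to the period before the burn or to the patient's current state. Either is acceptable as a covariate, since Section 5.1 has baseline data collected before randomization.
- **Description.** By-arm summaries may stay as description. If proportions of patients meeting the limit are shown, name one reference visit and compare the proportions between supplement and control.

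This costs a few sentences and needs no new data or model. The price is candour about precision: with 24 patients the intervals will be wide, about ±6.4 to ±9.6 points under the SDs assumed above and no loss to follow-up or covariate gain, and will rarely support a claim of clinical improvement.
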